#### Anticipated Attrition

As noted above, we will need a total of approximately 435 randomized subjects (N=145 per group) across all three study sites that meet criteria for prolonged abstinence through 1-year follow-up in order to have adequate statistical power to detect anticipated group differences in our primary and secondary endpoints. In order to achieve an effective sample-size of N=435 several levels of ineligibility and attrition must be considered. Overall we estimate that we will need to enroll approximately 1267 participants across all three sites into the study. Of the 1267 participants recruited, we anticipate that N=570 (45%) will be abstinent at the end of the open label cessation phase and eligible for randomization. Of those randomized we anticipate that 10% (N=57) will discontinue study participation prior to 1-year and an additional 15% (N=78) will relapse to smoking. Therefore, as outlined in Figure 2, we anticipate that a total of 1267 participants enrolled in the initial smoking cessation phase will result in an effective sample-size of approximately 435 (145 per group). Considerable effort will be made in an attempt to reduce the actual amount of attrition to less than that estimated. The Iowa site is responsible for attaining 500 of the 1267 participants. From statistics at the other recruiting sites, we estimate that the Iowa City site will have to screen approximately 912 participants in order to have 500 eligible for the cessation phase of the study.

Figure 2. Participant Flow and Attrition.

## XII. Future Research

XII.1 *Do you wish to keep any information about subjects involved with this research project so that members of the current research team may contact them in the future for your own research projects?*  
No

XII.2 *Do you wish to keep any information about subjects involved with this research project so that other researchers may contact them for future research?*  
No

XII.4 *Does this project involve storing any data, tissues or specimens for future research?*

No

### XIII. Other Mod and/or Comments

XIII.1      *Most modifications should be made in the appropriate section (see Index) of the project itself. If you need to describe other changes, or wish to add comments about something you changed, please do so here.*

XIII.2.      *Have you permanently stopped enrolling new subjects into this study?*  
Yes

### XIV. P&T / MRPC / RBC Mod Checklists

XIV.1      *Are any new drugs being added?*  
No

XIV.4      *Is either dose or duration of therapy changing?*  
No

XIV.7      *Have new risks been identified (new adverse reaction, new interaction, new toxicity)?*  
No

XIV.10      *Have there been any changes to the Investigator's Brochure or package insert?*  
No

Data Analytic Plan

Study Title: Blood Pressure Control in Hypertensive Smokers

NCT: NCT00113074

Approval Date: 09/20/2021

Treatment and Prevention Study Data Analytic Plan

Overview:

The main statistical analyses will be for the three-group randomized clinical trial with the primary analyses restricted to participants that do not relapse to smoking. Participants who discontinue study participation will be assumed to have relapsed to smoking. Therefore, analyses will be restricted to those with available data.

The primary efficacy endpoints are BP and body weight. Since the aim is to evaluate long-term efficacy, the primary analysis will evaluate treatment effects at 1-year. Analyses will also be conducted to assess changes in BP and body weight at six months. The primary analysis will be restricted to participants that have not relapsed to smoking and who provide follow-up data. Secondary analysis will be performed using all participants. The primary analysis will be performed using ANCOVA to assess for treatment effects adjusting for the baseline value of the dependent variable, study site, and any baseline variables found to differ significantly between groups. In all cases, each of the two experimental groups will be compared to the UL group. Since there are two pair-wise treatment comparisons of interest (BPC vs. UL; WGP vs. UL), we will utilize Fisher's least significant difference (LSD) approach to protect against inflation of the experimentwise error rate. An initial omnibus test will be used to test the null hypotheses that all group means are equal. Rejection of the null hypothesis will result in subsequent pair-wise comparisons between treatment groups. Conversely, if the null hypothesis associated with the omnibus test is not rejected, pair-wise comparisons will not be necessary.

Secondary endpoints will include servings of fruits and vegetables per day, dietary fat intake (% of total energy from fat), overnight urinary chloride excretion (mmol/day), and self-reported physical activity (kcal/kg/day). The analyses for the secondary endpoints will be similar to that for the primary endpoints, with groups compared using ANCOVA to assess for treatment effects adjusting for baseline values, study site, and baseline variables found to differ significantly between groups. In all cases, each of the two experimental groups will be compared to the UL group.

Relapse to tobacco use will be analyzed as an exploratory endpoint. At every contact following randomization subjects will be assessed for relapse to tobacco use, with relapse defined as using tobacco on seven consecutive days or using tobacco at least one day per week on two consecutive weeks. This definition is consistent with that proposed by the Society for Research on Nicotine and Tobacco (Hughes et al., 2003). For subjects that relapse, the date of relapse will be defined as the first day of tobacco use in the 7-day or 2-week period. Subjects that discontinue study participation prior to the 1-year follow-up visit, who have not already met relapse criteria, will be assumed to have relapsed to using tobacco. For these subjects, the date of relapse will be assigned as the day following their last study visit. Time to relapse will be analyzed using Cox proportional hazards regression (PROC PHREG) with time to relapse as the dependent variable and intervention group as the independent variable. For subjects that do not relapse to using tobacco, the time to relapse will be censored as of the date of their 1-year follow-up visit. Additional multivariable analyses assessing characteristics associated with relapse to tobacco use will be considered. However, these analyses will be considered exploratory in nature since our ability to perform meaningful multivariable analyses will be dependent on the number of subjects that relapse to tobacco use.

A number of additional analyses will be performed to describe the study characteristics and assess comparability between study groups. Participant adherence will be assessed as percentage of contacts completed and compared between groups using the rank sum test. The percentage of subjects that use other products (or programs) for smoking cessation, blood pressure or weight control will be summarized separately and compared between intervention groups using Fisher's exact test. Changes in hypertension status will be noted and coded as: -1=decrease in status, 0=no change, +1=increase in status; and changes in hypertension medication status will be noted and coded as: -1=decrease in medication, 0=no change, +1=increase in medication. Using these coded variables, changes in hypertension status and medication status will be compared across treatment groups using the Kruskal-Wallis test.

Analyses for phase 1 (smoking cessation):

Although the primary analyses are for the randomized trial, the first phase of this investigation (open-label smoking cessation phase) will provide meaningful data regarding smoking cessation efforts for individuals. For this phase, the primary outcome will be prolonged tobacco abstinence at the final program session (session 4) defined as self-reported abstinence from all tobacco (not even a puff) for the last 14 days, confirmed by expired CO<10 ppm. The percentage of participants that discontinue the program prior to the 4th session will be summarized along with the reason for discontinuation. The overall abstinence rate at the end of the program will be summarized using a point estimate and 95% confidence interval, with subjects that discontinue study participation assumed to be smoking. In addition, logistic regression will be used to perform exploratory analyses to assess potential participant characteristics associated with abstinence at the end of treatment. Participant characteristics considered in this analysis will include: age (years), gender, smoking rate (cpd), and level of nicotine dependence (FTND).

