## VII.E. Project Description (E)

VII.E.1	Will subjects be randomized?
	Yes
VII.E.2	Describe randomization scheme/assignment including ratio such as 1:1, 2:1 etc.
	Subjects who are able to quit smoking will be randomized to one of three lifestyle interventions according to a 1:1:1 ratio. The random allocation to conditions was conducted by a biostatistician, who placed each assignment in sequentially numbered and sealed envelopes. For each eligible participant who successfully quits smoking, randomization is done by opening the next available envelope, which has a 1 in 3 chance of getting assigned to each of the three interventions: Weight Gain Prevention, Blood Pressure Control, and Usual Care. The randomization assignment will be recorded on the randomization log.
VII.E.3	Will any questionnaires, surveys, or written assessments be used to obtain data directly from subjects in this study?
	Yes
VII.E.4	List all questionnaires, surveys, written assessments and ATTACH each one to the application. (NOTE: You are NOT prohibited from attaching copyrighted materials to this application)
	Participant contact form
	Participant demographics
	History of tobacco use
	Fagerstrom Test for Nicotine Dependence and Stage of Change
	Physical Activity Readiness Questionnaire
	Rose Angina Questionnaire
	Quick food scan – Fruits & Vegetables
	Quick food scan – Dietary fat
	Urinary chloride collection and monitoring forms
	International Physical Activity Questionnaire (IPAQ)
	Smoking Self-Efficacy
	Smoking Decisional Balance
	Weight Efficacy Lifestyle Questionnaire
	Weight Decisional Balance
	Weight Concerns Scale
	Exercise Confidence Survey
	Exercise Decisional Balance
	Treatment Evaluation I
	Treatment Evaluation II
	Health and Lifestyle Questionnaire – 6 Months
	Health and Lifestyle Questionnaire – 12 Months

VII.E.5 **Does this project involve creating any audiotapes, videotapes, or photographs?**  
Yes

VII.E.6 **Provide a detailed description in sequential order of the study procedures following the consent process - DO NOT cut and paste from the Consent Document.**

**Describe study populations separately if they will be participating in different procedures - include CONTROL population if applicable.**

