##### 1. Weight Gain Prevention Intervention

There have been several successful behavioral trials that targeted weight control and/or nutritional modification for the control of Blood Pressure including the multi-center clinical trial TONE; Trials of Nonpharmacologic Interventions in the Elderly. The Weight Gain Prevention intervention used in this study was derived from the Weight Loss Only program developed for TONE. The focus of the intervention will be on preventing weight gain following smoking cessation. Because participants will enter the study at a wide range of body weights, the emphasis will be on preventing the weight gain that accompanies quitting smoking rather than weight loss per se. Each participant will be provided with a copy of The CalorieKing Calorie, Fat & Carbohydrate Counter 2007 Edition, published by Dietclub.

Participants will be advised to engage in 30 minutes or more of moderate intensity activity on most, and preferably all, days of the week. Moderate intensity activities include those that range from 3.0 to 6.0 METS, or 4 to 7 kcal x minute-1. Examples include brisk walking, cycling at moderate speed, and general household cleaning. Participants will be given flexibility in both the specific types of moderate activity they choose to engage in, as well as the method in which they choose to accumulate their activity over the course of the day (e.g., several short bouts of activity vs. a single 30-minute period of exercise).

The Weight Gain Prevention intervention will consist of five individual and 12 group sessions lasting 30-60 minutes conducted over a 12-week period. Sessions will be held in person, but can be made up over the phone if the participant is unable to attend a session. As noted above, the intervention is modeled after the TONE Weight Loss Only protocol. The group sessions, which are largely didactic in format but also include group discussion, address a variety of proven weight management strategies including nutrition education, behavioral skills training, problem solving, "relapse" prevention, and moderate increases in physical activity. Participants also will be instructed to self-monitor their dietary intake and physical activity as a means of gaining additional insight into their behavior patterns, as well as to evaluate success in meeting behavioral goals.

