Each of the individual sessions will focus on reviewing participants' success with meeting dietary, physical activity, and weight goals, and problem solving strategies for increasing adherence and success. Consequently, these sessions will provide more specific, individualized instruction tailored to the needs of each individual participant.

At each session a small snack will be provided to the participants, prepared by the bionutrition department of the General Clinical Research Center (GCRC). The snacks will be designed to be low calorie, nutrient dense, and will illustrate the principles of what is being discussed at the intervention.

At all sessions, tobacco use status, serious adverse event information, and weight will be recorded. At the individual sessions, the participant will be asked about concomitant medications (smoking cessation, weight management, and blood pressure medications only), followed by an expired air carbon monoxide (CO) assessment, and a blood pressure reading. The weight gain prevention intervention portion of the study including 12 group sessions and 5 individual sessions will take approximately 17 hours to complete.

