As with the Weight Gain Prevention the primary rationale for incorporating increases in physical activity is for the weight controlling effects (Blair, 1993; Grilo et al., 1993). However, studies also have demonstrated hypotensive benefits from physical activity that are independent of weight loss (Arroll & Beaglehole, 1992; Whelton et al., 2002). Thus, physical activity appears to provide multiple benefits in terms of BP control, and will comprise an important component of the intervention. Because several studies have shown strength training to be effective at reducing BP (see Kelly & Kelly, 2000 for review), participants also will be encouraged to engage in resistance training as well as aerobic activities. Participants will be given flexibility both in the specific types of moderate activity they choose to engage in, as well as the method in which they choose to accumulate their activity over the course of the day (e.g., several short bouts of activity vs. a single 30-minute period of exercise).

The BP Control Intervention will consist of five individual and 12 group sessions lasting 30-60 minutes conducted over a 12-week period. Sessions will be held in person, but can be made up over the phone if the participant is unable to attend a session. As noted above, the intervention will be modeled after the TONE Weight Loss + Sodium Restriction protocol. Individual sessions will focus on reviewing participants' success with meeting treatment goals and problem solving strategies for increasing adherence and success. Consequently, these sessions will provide specific, individualized instruction tailored to the needs of each participant. The group sessions will address a variety of proven educational and behavioral strategies for modifying diet and physical activity. Several of the intervention components involve strategies similar to those included in the smoking cessation intervention (e.g., self-monitoring, problem solving, relapse prevention). Attempts will be made to emphasize these similarities and to build on previous mastery experiences as a means of promoting continuity across intervention components and enhancing self-efficacy.

At each session a small snack will be provided to the participants, prepared by the bionutrition department of the General Clinical Research Center (GCRC). The snacks will be designed to be low calorie, nutrient dense, and will illustrate the principles of what is

being discussed at the intervention.

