### 3. Usual Lifestyle Condition

To determine the relative effectiveness of the Blood Pressure Control and Weight Gain Prevention interventions, results will be compared to participants assigned to a Usual Lifestyle condition. Participants in this group will receive self-help materials designed to help them manage their body weight and blood pressure. These will consist of two books published by Mayo Clinic Health Information: Mayo Clinic Healthy Weight for Everybody and Mayo Clinic on High Blood Pressure: Taking Control of Your Hypertension. However, they will not receive any additional instructions for making lifestyle changes other than they would normally receive from their primary care provider.

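### Two arms are treated partly in groups and the control arm is not, but the ANCOVA assumes independent participants; if session-group members share any effect, standard errors against Usual Lifestyle are too small

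*SAP*

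**What the plan says.** Allocation is individual. Protocol VII.E.2 states: "For each eligible participant who successfully quits smoking, randomization is done by opening the next available envelope".

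Delivery then differs by arm (Protocol VII.E.6, Interventions):

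- **WGP**: "five individual and 12 group sessions lasting 30-60 minutes conducted over a 12-week period". The group sessions are described as ones "which are largely didactic in format but also include group discussion", and a missed session "can be made up over the phone if the participant is unable to attend a session".
- **BPC**: "The BP Control Intervention will consist of five individual and 12 group sessions lasting 30-60 minutes conducted over a 12-week period". Phone make-ups are allowed here too. The didactic description is given for WGP only.
- **UL**: "Participants in this group will receive self-help materials designed to help them manage their body weight and blood pressure". These are two books; there are no study sessions.

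The analysis is the same in the SAP Overview and Protocol XI.1: "The primary analysis will be performed using ANCOVA to assess for treatment effects adjusting for the baseline value of the dependent variable". Study site and baseline variables that differ between arms are also adjusted for. An omnibus test comes first; if it rejects, BPC and WGP are each compared with UL under Fisher's LSD. The secondary endpoints use a similar ANCOVA. Neither document mentions session group, a mixed model, cluster-robust errors, an ICC or a design effect.

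**The concern.** This is a partially nested design: people are randomized one by one, then two of the three arms are treated in groups. Members of a group share a leader, a timetable and each other. If any of that carries through to blood pressure or weight at 1 year, outcomes within a group are positively correlated, and the mean of a grouped arm varies more than the ANCOVA residual suggests.

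Two things follow. Confidence intervals against UL are too narrow. The omnibus test, which is the only gate to the pairwise tests, rejects too often under the null hypothesis. Adjusting for site removes differences between sites but not between session groups within a site. The secondary endpoints inherit the same problem.

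**Working it through.** **1. The plan's own figures assume independence.** Inputs from Protocol XI.2: two-sided alpha 0.025, power 80%; SBP difference 5.3 and SD 14.5 mmHg; DBP 3.4 and 9.4 mmHg; weight 2.0 and 5.0 kg. The formula for independent participants is n per arm = 2 × [SD × (2.241 + 0.842) / difference]².

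| Endpoint | Formula | Rounded up | Noncentral t | Stated |
|---|---|---|---|---|
| SBP | 142.3 | 143 | 144 | 144 |
| DBP | 145.3 | 146 | 147 | 147 |
| Weight | 118.8 | 119 | 121 | 120 |

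The stated sizes reproduce with no allowance for clustering.

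**2. Effect on the standard error.** Let m be the number of analysed members per session group. The design effect is DE = 1 + (m − 1) × ICC in WGP and BPC, and 1 in UL. The variance of a difference from UL is proportional to DE + 1 instead of 2, so the true standard error divided by the ANCOVA one is √[(1 + DE)/2].

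- m = 4, ICC 0.01: DE = 1.03, ratio √1.015 = 1.007.
- m = 12, ICC 0.01: DE = 1.11, ratio √1.055 = 1.027.
- m = 4, ICC 0.05: DE = 1.15, ratio √1.075 = 1.037.
- m = 12, ICC 0.05: DE = 1.55, ratio √1.275 = 1.129.

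Both m and ICC are assumptions. Planned retention in the primary set is 435/570 = 76% (Protocol XI.2), so 8 analysed members imply about 8/0.76 = 10.5 randomized, and 12 imply about 16. That is why values below 8 are included.

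**3. Effect on error rates.** Simulation under equal means: 145 per arm, closed groups, no covariates, 432 residual degrees of freedom. Whole-LSD error is the chance that the omnibus test rejects and at least one comparison with UL is then significant. The SAP gives no level for either LSD step. The table therefore uses an omnibus level of 0.05 with pairwise 0.05, and with pairwise 0.025, the only alpha the documents state. Simulation error is about 0.1 percentage point.

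| ICC | m | SE ratio | Omnibus | Whole LSD, pairwise 0.05 | Whole LSD, pairwise 0.025 |
|---|---|---|---|---|---|
| 0 | any | 1.000 | 5.0% | 4.2% | 3.6% |
| 0.01 | 4 | 1.007 | 5.3% | 4.4% | 3.8% |
| 0.01 | 8 | 1.017 | 5.7% | 4.7% | 4.0% |
| 0.01 | 12 | 1.027 | 6.2% | 5.1% | 4.3% |
| 0.02 | 8 | 1.034 | 6.5% | 5.3% | 4.4% |
| 0.02 | 12 | 1.054 | 7.3% | 5.9% | 5.0% |
| 0.05 | 4 | 1.037 | 6.6% | 5.4% | 4.5% |
| 0.05 | 8 | 1.084 | 8.8% | 7.1% | 5.9% |
| 0.05 | 12 | 1.129 | 11.2% | 8.9% | 7.4% |

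With 0.025 at both steps, whole-LSD error is 2.0% at ICC 0, and 3.8% (m = 8) to 5.0% (m = 12) at ICC 0.05.

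**4. Rolling entry.** With 8 or 12 people present at a time, and correlation assumed to fall linearly with overlap in the 12-week course, standard errors should be 1.6-2.5% larger at ICC 0.01 and 8-12% larger at ICC 0.05. This is close to the closed-group result.

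**The case against.** The strongest reply is that the size is entirely assumed. No ICC, group size or closed/rolling structure is given; group formation may be described in the operations manual (Protocol VIII.2, part VIII), which is not available here. Several features point to a small ICC: five sessions are individual, missed sessions can be made up by phone, WGP groups are largely didactic, and the endpoint falls months after a 12-week programme. At ICC 0.01 the whole-LSD error is at most about 5.1%. With pairwise 0.025 it exceeds 5% only around ICC 0.05 with m of 6 or more. All of this stands, and it limits the point to a minor one. It does not restore independence: intervals are too narrow at any positive ICC, and only a model with a group term can show that the ICC is negligible.

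A reader might also infer that the trial is underpowered. The documents do not support that. Protocol XI.2 plans on change scores while noting that ANCOVA usually has more power. It raises the weight SD from a pooled 4.2 to 5.0 kg, and it calls the detectable differences for secondary endpoints conservative. These margins may offset clustering. They do not, however, correct an error rate or an interval width.

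A third objection is that replacing the primary model with all data in hand could look data-driven. That is fair, and it is why the fix sets the clustered model beside the planned ANCOVA.

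**Conclusion.** The point holds as a conditional one. The documents establish individual randomization, group delivery in two arms only, and an analysis with no session-group term. For any ICC above 0 with more than one analysed member per group, standard errors against UL are too small and the omnibus test exceeds its level.

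For m = 4 to 12 and 145 per arm:

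- Standard errors should be 0.7-2.7% larger at ICC 0.01 and 3.7-12.9% larger at ICC 0.05.
- Omnibus error is 5.3-6.2% and 6.6-11.2%.
- Whole-LSD error is 4.4-5.1% and 5.4-8.9% with 0.05 at both steps, or 3.8-4.3% and 4.5-7.4% with pairwise 0.025.

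The truth is probably near the low end. It would be tempting to quote the 9-11% figures as the trial's false-positive rate. They need ICC 0.05 with 8 to 12 analysed members per group, which nothing in the documents supports, and they refer to the omnibus gate, not to the two comparisons of interest. Severity is minor: a cheap improvement.

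**What to change.** Before analysis, add the following to the SAP:

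- Where session group can be identified from study records, fit a second model that keeps the planned ANCOVA fixed effects and adds a random intercept for session group in WGP and BPC only. Each UL participant is a cluster of one. Use small-sample degrees of freedom.
- Report the omnibus test, both pairwise tests and intervals, and the ICC from this model beside the planned ANCOVA, for primary and secondary endpoints. State that the model was added after data collection.
- Describe a claim against UL that holds only in the unclustered model as not robust to clustering.
- If membership was rolling, use site by arm by a start-date block of pre-specified length, and say that this is approximate.
- If no identifier can be recovered, state that the intervals assume no clustering.

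**Feasibility.** Protocol I.4 says only analysis and manuscript preparation remain. The documents do not say that session group was recorded. But the intervention text says: "At all sessions, tobacco use status, serious adverse event information, and weight will be recorded". The SAP also analyses the percentage of contacts completed. Site, arm and session date may therefore allow reconstruction, though phone make-ups weaken it.

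**Performance.** In simulations with m = 8 or 12 and ICC 0 to 0.05, the random-intercept model with closed groups held omnibus error at 3.8-5.6% and whole-LSD error at 3.3-4.8%. With rolling entry and 12-week blocks the ranges were 3.9-6.5% and 3.3-5.4%.

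**Cost.** Work to recover the identifier, slightly wider intervals, a documented late SAP change, and an imprecise ICC (estimated as zero in about 40% of simulated trials at a true ICC of 0.01). The enrolled sample does not change.
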